- The Laplacian Current Source Density transformation with an order of splines 4, the maximal degree of Legendre polynomials 10 and 1×10^{-5} Lambda was applied.
- The FFT with maximum resolution voltage, no window function, and complex output on the half spectrum was computed.
- The imaginary part of coherency was used to evaluate connectivity between hemispheres, within hemispheres, and midline connectivity.

● **MRI Acquisition**

- Philips Achieva 1.5 Tesla scanner was used.
- Scans were performed according to the Alzheimer's disease Neuroimaging Initiative (ADNI, www.adni.loni.usc.edu).
- The pre-processing of images was performed with the SPM12 software package.
- The gray matter volumes and cortical thickness were obtained from the 3D-T1 weighted TFE sequence (TR: 9ms, TE: 4ms, FOV: 240mm, matrix: 256, slice thickness: 1mm, NSA: 1).
- Mean gray matter volumes (GMVs) inside ROIs were estimated using the LPBA40.
- The total intracranial volume (TIV) for each participant is calculated and exported. GMVs were normalized according to each individual's TIV to remove the effect of different brain sizes.

STATISTICAL ANALYSIS PLAN (SAP)

- **For EEG Analysis:**

The following EEG measures were analyzed using separate repeated-measures ANOVA including group as a between-group factor and different within-subject factors for;

(1) the EEG power [*anterior-posterior distribution* (frontal, central, parietal, and occipital) and *laterality* (left, midline, and right)];

(2) EEG intra-hemispheric ICoh measures [*region* (14-levels) and *hemisphere* (left and right)];

(3) midline-to-lateral ICoh measures [*midline region* (4-levels), *lateral region* (8-levels) and *hemisphere* (2-levels)];

(4) midline-to-midline ICoh measures [*midline region* (3-levels)];

(5) inter-hemispheric ICoh measures [*region* (10-levels)].

All analyses were performed for total gamma and sub-gamma frequency bands.

When Mauchly's test indicated that the assumption of sphericity had been violated, the Greenhouse-Geisser correction was applied where $\varepsilon < 0.75$, and the Huynh-Feldt correction was applied where $\varepsilon > 0.75$.

- **For EEG Analysis:**

GMV measures were analyzed with univariate ANOVA. Age and gender variables were included in the analysis as covariates. Bonferroni correction was applied for 54 GMV ROIs. The significance level was set to $P < 0.0009$.

- **For Correlations Analysis:**

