Correlations between CSF, NPT, EEG, and MRI parameters were analyzed with Pearson correlation analysis. In order to minimize the number of false positives in correlation analysis, a Benjamin-Hochberg false discovery rate (FDR) was used to control the type-I error.

- **For Discriminant Analysis:**

The discriminant analysis was performed including the group as the dependent variable and a total of four independent variables (three electrode pairs from coherence and one electrode from power analysis) to the model. The analysis was performed with the enter method.

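### The single Bonferroni cut-off for the 54 GMV regions is valid, but Holm's step-down keeps the same guaranteed family-wise error, never loses a region and may find more

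*Combined protocol and SAP*

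**What the plan says.** The rule stands in the SAP, in the second of two paragraphs headed *For EEG Analysis*. The heading looks like a labelling slip, since the text concerns MRI volumes.

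- Test: "GMV measures were analyzed with univariate ANOVA".
- Adjustment: "Age and gender variables were included in the analysis as covariates".
- Multiplicity: "Bonferroni correction was applied for 54 GMV ROIs".
- Cut-off: "The significance level was set to" P < 0.0009, the same for every ROI.

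The SAP gives no overall alpha for this family, no step-down rule and no reason for preferring a single-step one. The only other multiplicity method is in the correlations paragraph, where a "false discovery rate (FDR) was used to control the type-I error". That covers the correlations only.

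**The concern.** A single-step rule holds every ROI to the same strict cut-off, however many of the others have already been rejected. Holm's procedure relaxes the cut-off after each rejection without weakening the guarantee on family-wise error. The study compares patients with early-onset Alzheimer's disease with healthy individuals. If volume differences are widespread across the 54 ROIs, a fixed cut-off fails to declare some true differences that Holm would declare at the same guaranteed error rate. At stake is how many regional differences are called significant, not whether those already called significant can be trusted.

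**Working it through.** **Inputs from the SAP.** Family size m = 54; fixed cut-off 0.0009; one ANOVA per ROI, adjusted for age and gender, read here as giving one group p-value per ROI.

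**Input assumed.** Overall alpha 0.05. It is not stated, but the cut-off implies it.

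**Step 1: reproduce the stated figure.** alpha/m = 0.05/54 = 0.000926, which is 0.0009 to four decimals. The union bound at the stated cut-off is 54 × 0.0009 = 0.0486. With independent tests the family-wise error is 1 − (1 − 0.0009)^54 = 0.0475.

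**Step 2: Holm's thresholds.** The i-th smallest p-value is compared with 0.05/(54 − i + 1), stopping at the first failure:

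| i | Holm threshold |
|---|---|
| 1 | 0.05/54 = 0.000926 |
| 2 | 0.05/53 = 0.000943 |
| 11 | 0.05/44 = 0.00114 |
| 21 | 0.05/34 = 0.00147 |
| 28 | 0.05/27 = 0.00185 |
| 41 | 0.05/14 = 0.00357 |
| 54 | 0.05/1 = 0.05 |

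Every threshold exceeds 0.0009. If k ROIs have P < 0.0009, the k smallest p-values all pass, so Holm rejects those k ROIs and possibly more. This holds for any data.

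**Step 3: size of the gain.** The documents give no sample size, effect size, number of affected ROIs or inter-ROI correlation, so all of these were assumed and varied: 15, 20 or 30 per group in two groups; a standardised difference of 0.8 or 1.2 in each affected ROI; 0, 10, 27 or 40 affected ROIs; correlation 0 or 0.5; 20,000 simulated studies per setting. Test statistics were drawn as t statistics with 2n − 4 degrees of freedom (n per group), which allows for two covariates; no covariate values were simulated. Ranges run over all settings in each row.

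| Affected ROIs | Studies where Holm finds more than P < 0.0009 | Mean extra true ROIs | Same two figures against unrounded 0.05/54 |
|---|---|---|---|
| 0 | 0.1-0.2% | none possible | 0-0.1%; none possible |
| 10 | 2.5-16% | 0.02-0.17 | 0.9-13%; 0.01-0.13 |
| 27 | 10-73% | 0.11-1.3 | 6-70%; 0.07-1.2 |
| 40 | 17-96% | 0.20-3.4 | 13-95%; 0.14-3.3 |

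The last column removes the effect of rounding 0.000926 down to 0.0009. The largest gain (20 per group, 1.2 SD, 40 affected, correlation 0) takes the mean number of true ROIs found from 22.9 to 26.3, that is, average power from 22.9/40 = 57% to 26.3/40 = 66%.

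**Step 4: realised family-wise error.** In settings with affected ROIs it was 0.010-0.042 under P < 0.0009 and 0.012-0.048 under Holm. The largest rise was from 0.011 to 0.039 (30 per group, 1.2 SD, 40 affected, correlation 0). With no affected ROI, Holm gave 0.035-0.051, the same as unrounded Bonferroni in the same runs. The simulation standard error near 0.05 is √(0.05 × 0.95/20,000) = 0.0015, so 0.051 is compatible with the 5% bound.

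**The case against.** The strongest reply is that nothing here is wrong. The SAP names the family, the method and the cut-off; the cut-off reproduces; and the method controls family-wise error under any dependence. Preferring another valid method may look like taste. The validity stands in full. The charge of taste does not: Holm dominates at the same guaranteed bound, with the same p-values and no further assumption.

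It is also fair to object that the gain rests on assumed inputs and can be close to nothing. That stands, and is why the full range is shown.

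A reader might infer more than the documents support:

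- *That Bonferroni assumes all 54 null hypotheses are true.* It does not. It controls the error whatever the number of true nulls, and is merely conservative when some are false.
- *That rounding to 0.0009 is a defect.* A bound of 0.0486 instead of 0.05 is ordinary rounding in the safe direction.
- *That Holm has no effect on false positives.* Only the guaranteed bound is the same; the realised rate is higher, as Step 4 shows.
- *That undeclared regions vanish from the report or distort later analyses.* Nothing says that non-significant ROIs go unreported. Nor does anything say that GMV significance selects variables for the correlations or for the discriminant model, whose four predictors are all EEG variables.
- *That the GMV family should use the false discovery rate because the correlations do.* That would control a different error rate and is a separate choice.

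**Conclusion.** The point holds as a missed efficiency in a valid plan. That Holm never loses an ROI found at P < 0.0009, within the same 5% guarantee, is a mathematical fact that needs no assumption beyond an overall alpha of 0.05. How much is gained depends on facts that the documents do not give. Under the assumed ranges the benefit is negligible if few ROIs differ: at most 0.17 extra true ROIs on average with 10 affected. It can be material if most differ: up to 3.4 with 40 affected, though only 0.20 at the low end. The power figures are illustrative, since they come from equally correlated statistics with equal effects and not from the study's data. Bonferroni findings under the stated rule need no retraction or re-reading.

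**What to change.** Replace the fixed cut-off in the GMV paragraph with Holm's procedure and state the overall alpha. Suggested content: the 54 group p-values from the age- and gender-adjusted ANOVAs are ordered; the i-th smallest is compared with 0.05/(54 − i + 1), stopping at the first failure; family-wise error is controlled at 0.05. Report for all 54 ROIs the Holm-adjusted p-value, which for the i-th smallest is the largest of min(1, (54 − j + 1) × p(j)) over j = 1 to i.

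The text change is a sentence or two, with no new data, model or assumption. The statistical cost is a somewhat higher realised family-wise error, still within 5%. There is also a reporting cost: the SAP is written in the past tense, so the GMV results may already be known. If they are, the planned Bonferroni result should be kept and the Holm-adjusted p-values shown beside it, labelled post hoc.

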07/25/2023

**THE UNDERESTIMATED UTILITY OF RESTING-STATE GAMMA
OSCILLATIONS: BOTH INCREASE AND DECREASE OF GAMMA
DISCRIMINATES EARLY-ONSET ALZHEIMER'S DISEASE PATIENTS FROM
HEALTHY INDIVIDUALS**

STUDY PROTOCOL:

- **EEG Recording and Analysis**

Instructions Prior to Experiment and EEG Recording Environment

- Participants were asked not to consume any caffeine prior to experiments.
- EEG was recorded in a sound-attenuated and electrically shielded room.

EEG Recording Setup

- EEG was amplified using a BrainAmp 32-channel DC amplifier
- EEG was bandpass-filtered between 0.03-70 Hz and digitized at a sampling rate of 500 Hz (Brain Products GmbH; Gilching, Germany).
- EEG was recorded from 30 Ag/AgCl electrodes (Figure 1).
- Electrodes were positioned on an elastic cap according to the international 10-20 system (EasyCap; Brain Products GmbH; Gilching, Germany).
- All electrodes were referenced to linked earlobes (A1+A2).
- Electrooculograms (EOG) were recorded from two additional electrodes.
- Electrode impedances were kept below 10 k Ω .
- EEG recordings were performed during morning hours (approximately between 09.00 to 10.00 am)
- EEG recordings lasted 8 minutes (4 minutes: eyes open & 4 minutes: eyes closed).

[figure not shown]

Figure 1. EasyCap layout for 30 Electrodes (EasyCap; Brain Products GmbH; Gilching, Germany)

EEG Data Preprocessing

Brain Vision Analyzer v.2.2 (Brain Products GmbH; Gilching, Germany) program was used for offline data analysis. EEG preprocessing was employed as below;

- The continuous EEG data were resampled to a 256 Hz sampling rate.
- A band-pass filter at 0.1 with a 12 dB/octave slope and a 50 Hz notch filter was applied.
- Vertical and horizontal ocular artifacts were corrected with independent component analysis (ICA) with the Infomax algorithm using default parameters.
- Four minutes eyes-closed recordings were segmented into six-second epochs.

- Artifacts that still contaminated the EEG data (i.e., muscle artifacts and drowsiness) were semi-automatically rejected based on maximum voltage steps of 50 $\mu\text{V}/\text{ms}$, amplitudes exceeding $\pm 70 \mu\text{V}$, and activity below 0.5 μV parameters.

Power Spectral Analysis

A Fast Fourier Transform (FFT) was applied with

- Maximum resolution power,
- Non-complex output on full-spectrum,
- 10% Hanning window function

Coherence Analysis

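### The discriminant analysis enters four unnamed EEG variables with no stated basis, validation or performance measure, so any accuracy computed as written is in-sample and optimistic on average

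*Combined protocol and SAP*

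**What the plan says.** The SAP section on discriminant analysis is two sentences long.

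- Outcome: "The discriminant analysis was performed including the group as the dependent variable".
- Predictors: "a total of four independent variables (three electrode pairs from coherence and one electrode from power analysis) to the model".
- Entry: "The analysis was performed with the enter method".

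No pair, electrode or frequency band is named, there or elsewhere. Nothing says how the four were arrived at. No hold-out sample, cross-validation or external sample is mentioned, and no accuracy, sensitivity, specificity or AUC is defined. The gap is not a redaction or a missing figure.

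Two other places bear on the point. The SAP's first section headed For EEG Analysis sets out the power and imaginary-coherence (ICoh) measures and adds that "All analyses were performed for total gamma and sub-gamma frequency bands". The title says that a rise and a fall in gamma "DISCRIMINATES EARLY-ONSET ALZHEIMER'S DISEASE PATIENTS FROM" healthy individuals.

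**The concern.** A discriminant function is fitted to make the groups in hand look as different as possible. If it is then scored on the people it was fitted to, the accuracy is on average higher than it would be in new people. This holds for four variables fixed in advance. It is made worse if the four were first picked because they separated these same groups.

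The document is written in the past tense and its title already states the result, so it does not show that the four were fixed beforehand. It does not show the opposite either.

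This is the only planned analysis with group as the dependent variable, so it is where a claim about classifying individuals would have to come from. As written, a reader could not tell how well new people would be classified. The SAP guards against chance findings elsewhere (Bonferroni for the 54 grey-matter regions, a false discovery rate for the correlations) but states no comparable safeguard here.

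**Working it through.** The section states no accuracy, sample size or power, so there is no figure to reproduce. The check asks how far in-sample accuracy would sit above accuracy in new people.

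**Inputs from the SAP's EEG section (cells per band)**

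- Power, "frontal, central, parietal, and occipital) and *laterality* (left, midline, and right": 4 × 3 = 12.
- "EEG intra-hemispheric ICoh measures [*region* (14-levels) and *hemisphere* (left and right": 14 × 2 = 28.
- "midline-to-lateral ICoh measures [*midline region* (4-levels), *lateral region* (8-levels) and *hemisphere* (2-levels": 4 × 8 × 2 = 64.
- Midline-to-midline 3; inter-hemispheric 10.
- Coherence total: 28 + 64 + 3 + 10 = 105. All cells: 105 + 12 = 117 per band. The number of sub-bands is not stated.

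**Assumed, because the documents do not say:** 15 to 100 per group, equal groups, normal data, exchangeable correlation of 0 to 0.8, standardised effects d, each cell a candidate variable, and (for the selected case only) a rule that takes the three coherence cells and one power cell with the largest |t|.

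**Formulas.** With group means m0 and m1 and pooled covariance S, the weights are w = S⁻¹(m1 − m0) and the cut is c = w′(m0 + m1)/2.

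- In-sample accuracy is the share of the same 2n people on the correct side of c.
- New-subject accuracy is ½Φ((c − w′μ0)/s) + ½Φ((w′μ1 − c)/s), with μ0, μ1 the true group means and s = √(w′Σw).
- The gap is the first minus the second, averaged over simulated data sets.

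**A. Four fixed in advance, independent predictors**

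| Per group | No difference: in-sample (true 50%) | d = 0.5: in-sample | d = 0.5: new | Gap (points) |
|---|---|---|---|---|
| 15 | 65% | 74% | 65% | 9 |
| 20 | 62% | 73% | 66% | 7 |
| 30 | 60% | 72% | 67% | 5 |
| 50 | 58% | 71% | 68% | 3 |
| 100 | 55% | 70% | 68% | 1 |

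As a sanity check, four independent variables with d = 0.5 have a Mahalanobis distance of 0.5 × √4 = 1, so the best attainable accuracy is Φ(1/2) = 69%. In-sample values lie above this and new-subject values below it. Leave-one-out gives 65% to 68%, close to the new-subject column. With correlation 0.5 the gap is larger: 67.7% − 58.4% = 9 points at 20 per group, and about 11 at 15.

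**B. Four selected from these data, one band, no true difference (true 50%), 30 per group**

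| Correlation | In-sample | Leave-one-out on the chosen four | 10-fold, selection inside each fold |
|---|---|---|---|
| 0 | 74–75% | 70% | 51% |
| 0.5 | 67–68% | 62% | 49% |
| 0.8 | 63% | 55% | 50% |

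With an assumed four bands the in-sample range is 64% to 78%.

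**C. Four selected, real effect on 10 of 105 coherence and 2 of 12 power cells**

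| d | Correlation | Per group | In-sample | New | Gap (points) |
|---|---|---|---|---|---|
| 0.5 | 0 | 30 | 79.8% | 64.0% | 16 |
| 0.5 | 0.5 | 30 | 72.3% | 60.4% | 12 |
| 0.8 | 0 | 30 | 86.7% | 77.5% | 9 |
| 0.8 | 0.5 | 30 | 76.4% | 68.1% | 8 |
| 0.8 | 0.8 | 50 | 70.5% | 66.4% | 4 |
| 0.8 | 0.8 | 100 | 68.5% | 66.5% | 2 |

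In the first row, leave-one-out on the chosen four gives 76% and nested 10-fold gives 64%; only the nested figure matches new subjects.

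**The case against.** **The four may have been fixed in advance.** They may, and nothing in the documents excludes it. A reader might infer, from the past tense and the result-stating title, that they were picked from the group comparisons. The documents do not say so, and tables B and C apply only if it happened. Table A does not need that premise.

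**The enter method avoids selection.** It avoids stepwise selection inside the model and is no fault. It does not tell us how four variables were reached from the candidates.

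**The SAP promises no accuracy.** This is a fair limit. Increases and decreases in gamma are group differences, which the ANOVAs address. An overall Wilks or Hotelling test on a pre-fixed four is valid without cross-validation; in simulation it rejected a true null 4.5% to 5.3% of the time. If only that were reported, the optimism would not arise. But such a test shows that the groups differ, not how accurately a new person is classified.

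**The bias may be small.** This stands in part. It is tempting to say that the optimism is modest for a fixed four and large for a selected four. The figures do not support that as a general contrast. With no true difference, 30 per group and correlation 0.8, selection adds only 63.3% − 60.1% = about 3 points. A selected four can have a gap of 2 points (last row of table C), while a fixed four can have one of 9 (d = 0.5, correlation 0.5, 20 per group).

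**In-sample accuracy is not always too high.** Correct. With a fixed four and a real effect it exceeded true accuracy in 70% to 92% of simulated data sets, depending on the scenario. The claim concerns the average.

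**Conclusion.** The concern holds as an omission with a known direction. Any classification accuracy computed from the section as written is in-sample and optimistic on average, whether or not the four were fixed beforehand. If they were selected from the same participants, there is further optimism, and leave-one-out applied afterwards does not remove it.

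The size cannot be taken from the documents. Under the stated assumptions the gaps are about:

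- Fixed four, no true difference: 15 down to 5 points (15 to 100 per group).
- Fixed four, d = 0.5: 1 to 11 points (15 to 100 per group, correlation 0 to 0.5).
- Selected four, no true difference: 13 to 25 points (30 per group, one band, correlation 0.8 to 0).
- Selected four, d = 0.5 to 0.8: 2 to 16 points (30 to 100 per group, correlation 0 to 0.8).

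These are illustrations, not bounds; at 20 per group the last case reached 23 points. Confidence is high for the omission and the direction, not for the size. A reader should not infer that the groups do not differ, or that the discriminant analysis is invalid as a test of difference. The point should be fixed because the remedy is cheap and the title rests on discrimination; it does not undermine the study as a whole.

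**What to change.** 1. Name the three pairs, the power electrode and the band of each, and state how and when they were chosen.
2. Name the performance measures: accuracy, sensitivity and specificity, with confidence intervals.
3. Estimate them by leave-one-out, stratified 10-fold cross-validation or an equivalent bootstrap optimism correction. If the four were fixed before group differences were seen, give the basis; ordinary cross-validation then suffices. If a rule chose them from these data, write the rule down and repeat it, with any data-driven choice of band, inside every fold or resample.
4. If they were chosen by judgement after the data were seen, label that model exploratory pending independent data. A nested result for a rule written afterwards can be reported, but it does not validate the original choice.
5. In all cases label in-sample accuracy as optimistic and secondary.

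Naming the variables alone would repair the description but not the estimate; the validation step does that.

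The cost is a few lines of SAP text and, since the analysis appears to have been done, probably a short reanalysis of existing data. The reported accuracy will on average be lower. A written rule may also return a different four, and confirming a judgement-based model would need new participants.
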